### 6.5 Data Analysis

Statistical analyses will be performed using statistical analysis software to determine the correlation between changing hemoglobin concentrations determined by the 3 different methods and spectral absorbance. ORI data will also be analyzed to determine any correlation with PaO2 obtained by ABG. PVI data will be correlated to SVV. Outcome data will be analyzed for any relationships between the inciting event, blood loss and outcome markers to evaluate for any predictive value of inciting factors and any correlation between transfusion and fluid management variables on outcome.

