**Validation of a pulse oximetry based hemoglobin measurement system. Comparison of plethysmographic variability index to standard methods of guiding fluid and transfusion management in the critically ill adult patients. Validation of Clinical Efficacy of ORI for supplemental oxygen titration.**

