## **1.3 Risk/Benefits**

The major risks to the patient are related to the surgical procedure, prolonged intubation or initial reason for ICU admission (bleeding, infection, pain, etc). Participation in this protocol places the patient at minimal if any additional risk. Additional blood sampling with each ABG analysis or CBC represents only 0.1% of the estimated blood volume of a 15 kg child and a much smaller percentage in larger patients. The maximum additional volume removed for sampling in one subject (40 mL) represents approximately 3.4% of the estimated blood volume of a 15 kg child and a much smaller percentage in larger patients. It is expected that many subjects will have fewer than 10 blood samples ordered by the ICU care team that would be used for data collection in this study. The small additional volume needed for sampling will not adversely impact the patient. The additional blood volume removed for testing purposes will not be large enough to change transfusion decisions. Pulse oximeters are commonly utilized devices that are considered to be minimal risk. There is theoretically an extremely small risk of damage to the subject's fingers from the device including potential mild allergic reaction to sensor material and adhesives, temporary skin irritation or discomfort associated with exposure to the sensor.

There are no direct benefits to the subject from participation in this protocol. Possible future benefits to society or other patients may occur if the system is shown to be accurate enough to be used in place of invasive determination of Hb or PaO2 in critically ill adult patients.

**Safety parameters:** Case report forms will be analyzed quarterly by the internal review process of the Department of Anesthesiology/Critical Care Center Research Division. Any adverse events related to protocol participation will be reported to the IRB. In addition, all adverse events will be reported to the sponsor.

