## **2 STUDY DESIGN**

This is a sponsored, prospective, nonrandomized, sequential data collection study to be performed in anemic adult patients who are admitted into the Surgical Intensive Care Unit (SICU/8100), Cardiothoracic Intensive Care Unit (CTICU/7100) or Neuro-Multidisciplinary Critical Care Services (NMCCS 8100 or 9100). Noninvasive pulse oximetry-determined SpHb will be compared to ABG co-oximetry and research lab equipment-determined Hb values, Oxygen Reserve Index (ORI) will be correlated with paO2 via ABG, PVI and acoustic waveform data will be compared to the arterial waveform extracted SVV or PPV values. The study goal is to establish the correlation of Hb values determined by the SpHb system with Hb as measured by other validated devices, use ORI to correlate with paO2 in the moderate hyperoxic regions and correlation of PVI with SVV or PPV values.

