### 6.3 Sample Collection

Each patient enrolled in this trial will have Hb measured and recorded prior to data collection. SpHb data will be obtained continuously or via spot check in SICU/8100, CTICU/7100 or NMCCS 8100 or 9100. During spot checks, blood samples must be obtained simultaneously with noninvasive reading and will thus be coordinated. SpHb will be recorded with each blood draw sample. Additional blood sampling is necessary to validate the SpHb system. For patients over 15 kg weight, at each standard of care ABG sampling an additional 4 mL of blood will be collected for patients in the SICU/8100, CTICU/7100 or NMCCS 8100 or 9100 and sent for cell count and cyanomethemoglobin determination by Masimo laboratories. These additional samples will be obtained to a maximum of 10 ABG samples per patient, only when ordered by ICU team. Thus up to 40 mL total additional blood volume may be obtained in one subject. Blood samples will be inverted or rolled 10 times to ensure proper mixing to prevent micro clotting. Patients less than 15 kg will not have any additional blood sampling done at the time of ABG analysis. All decisions regarding fluid management and the need for transfusion will be at the discretion of the attending physicians caring for the patient and will be based on the results of the clinical status and Hb measured by CBC as is customary for transfusion. The time of the CBC draw and corresponding blood samples will be noted as part of the data collection for validation of the system.

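### In the available text, correlation is the only SpHb analysis named, and correlation cannot show the agreement with reference Hb that a validation study needs

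*Combined protocol and SAP*

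**What the plan says.** Two places describe how SpHb will be assessed.

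- Section 2 says "Noninvasive pulse oximetry-determined SpHb will be compared to ABG co-oximetry and research lab equipment-determined Hb values" but gives no metric. It then states: "The study goal is to establish the correlation of Hb values determined by the SpHb system with Hb as measured by other validated devices".
- Section 6.5 says the analyses will "determine the correlation between changing hemoglobin concentrations determined by the 3 different methods and spectral absorbance". It does not list the three methods and does not mention SpHb by name.

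Three other places describe what the study is for.

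- The title: "Validation of a pulse oximetry based hemoglobin measurement system".
- Section 6.3, on why extra blood is drawn: "Additional blood sampling is necessary to validate the SpHb system".
- Section 1.3, on possible future benefit if the system is "shown to be accurate enough to be used in place of invasive determination of Hb".

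Sections 2 and 6.3 mention four possible references: ABG co-oximetry, cell count, cyanomethemoglobin and CBC. None is named as the main one. On repeated measurement, Section 6.3 says "These additional samples will be obtained to a maximum of 10 ABG samples per patient". In the text available, no section names bias, limits of agreement, root-mean-square error, an accuracy margin for SpHb, or a way to handle repeated pairs from one patient.

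**The concern.** Whether a device is valid, or accurate enough to stand in for another measurement, depends on how far its readings fall from the reference in g/dL. Correlation measures how closely the points follow some straight line, not whether that line is the line of identity. A device that reads high by a fixed amount, or that stretches or compresses the scale, can still correlate strongly. Correlation also rises when the enrolled patients span a wider Hb range, with no change in the device.

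The harm is to inference, not to subjects. Section 6.3 bases transfusion decisions on clinical status and CBC Hb, not on SpHb. But a team that followed the stated analysis exactly would finish with a coefficient that does not answer the question in the title. Agreement could be computed later from the same pairs. The reference, the metric and any margin would then be chosen with the data in hand.

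**Working it through.** The documents give no SD, margin, power or expected correlation, so there is no plan figure to reproduce. The documents supply only the maximum of 10 additional samples per patient. The other inputs are assumptions for illustration: reference Hb with mean 9.5 and SD 1.5 g/dL, and SpHb random error with SD e = 1.0 g/dL.

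**1. Constant offset.** With slope 1, r = SD_Hb / √(SD_Hb² + e²) = 1.5 / √(2.25 + 1.00) = 0.832. The offset does not appear in this formula. Limits of agreement are offset ± 1.96 × 1.0, and root-mean-square error is √(offset² + 1.0²).

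| Offset (g/dL) | r | 95% limits of agreement | RMSE |
|---|---|---|---|
| 0 | 0.832 | −1.96 to 1.96 | 1.00 |
| 1 | 0.832 | −0.96 to 2.96 | 1.41 |
| 2 | 0.832 | 0.04 to 3.96 | 2.24 |

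A simulation of 2,000,000 pairs gave the same values.

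**2. Proportional error.** Let the device have slope b around the mean, with random error fixed at 1.0. Then r = 1.5b / √((1.5b)² + 1), and the SD of differences is √((1 − b)² × 2.25 + 1).

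- b = 1.0: r = 0.832, SD of differences 1.00.
- b = 1.3: r = 1.95 / √(3.80 + 1) = 0.890, SD of differences √(0.09 × 2.25 + 1) = 1.10. Bias is 0.3 × (Hb − 9.5), so the device reads 0.75 low at Hb 7 and 0.75 high at Hb 12.
- b = 0.7: r = 0.724, with the same SD of differences, 1.10.

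If the random error is instead scaled by the slope, b = 1.3 leaves r at 0.832. The SD of differences becomes √(0.2025 + 1.69) = 1.38, and the limits widen to ±2.70. Under one model r rises and under the other it does not move. In both, agreement is worse and r does not show it.

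**3. Spread of Hb.** Keep the error SD at 1.0.

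- Hb uniform over 7–10: SD 3/√12 = 0.866, r = 0.65.
- Hb uniform over 7–15: SD 8/√12 = 2.309, r = 0.92.

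The differences are the same in both cases. Varying the Hb SD over 1.0–2.5 and the error SD over 0.7–1.3 gives r from 1.0/√(1 + 1.69) = 0.61 to 2.5/√(6.25 + 0.49) = 0.96.

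**4. Repeated pairs.** This step concerns the analysis that would replace correlation. For m pairs per patient and within-patient correlation ρ of the differences, a 95% CI for mean bias that ignores clustering is too narrow by √(1 + (m − 1)ρ). Its approximate true coverage is 2Φ(1.96/factor) − 1.

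| ρ (assumed) | Factor, m = 10 | Coverage, m = 10 | Factor, m = 4 | Coverage, m = 4 |
|---|---|---|---|---|
| 0.3 | 1.92 | 69% | 1.38 | 84% |
| 0.5 | 2.35 | 60% | 1.58 | 78% |
| 0.7 | 2.70 | 53% | 1.76 | 73% |

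Simulation with 100 patients and 10 pairs each (2,000 runs) gave 68%, 59% and 52% for the interval that ignores clustering, and 94–95% for a patient-level interval. Ten is the cap on the additional samples. Section 1.3 expects many subjects to have fewer, and m = 4 is an assumed smaller case.

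**The case against.** The strongest counter-argument is that the Section 6.5 sentence may not concern SpHb validation at all. It relates Hb to spectral absorbance, which could describe sensor development: Section 1.2 describes capture of wavelength data, Section 5 includes prototype sensors, and Section 6.6 has the sponsor's engineers analyse the data. The ambiguity is real, and the text should be clarified. It does not rescue the plan. On that reading Section 6.5 contains no analysis of displayed SpHb, and the Section 2 goal, which does name SpHb, is still correlation.

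Section 2 also promises a comparison with reference Hb, so agreement is not ruled out. But no metric is given, and the next sentence states the goal as correlation. Section 3 was not in the text available for review, so statements here about what is absent are limited to what could be read. If Section 3 does define an agreement analysis, Section 6.5 and the goal sentence still need to match it.

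One can also argue that this is a nonrandomized data-collection study with no stated hypothesis test. Replacing invasive Hb is only a conditional future benefit, and the data remain usable for agreement. All of that stands, and it limits the consequence to inference. It does not change the fact that the named statistic cannot answer the validation question.

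**Conclusion.** The point holds: the SpHb analysis is wrong as written and must be corrected before the study can support a validation statement. That r is unaffected by a constant offset is algebra and needs no assumption. The sizes rest on the assumed SDs. With those, a device reading 2 g/dL high gives the same r (0.83) as an unbiased one, while root-mean-square error goes from 1.0 to 2.2 g/dL. The same device error yields r of 0.65 or 0.92 depending only on the Hb range enrolled. The clustering figures depend on the assumed within-patient correlation and on how many pairs patients contribute. They show why the replacement analysis needs a clustered method, not an error in a calculation the plan contains.

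**What to change.** Change Section 6.5 and the goal sentence in Section 2 as follows.

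- Make the main SpHb analysis the agreement of the displayed SpHb value with one named reference. Cyanomethemoglobin on the paired 4 mL sample is one candidate, with ABG co-oximetry and CBC as secondary references.
- Define the pair. Section 6.1 allows up to eight sensors, so say which sensor and site supply the main value. Section 6.3 records SpHb at every blood draw, so say which draws count; the cap of 10 covers only the additional samples.
- Report mean bias, SD of differences, 95% limits of agreement and root-mean-square error. Check for proportional bias by relating the difference to Hb level.
- Use limits and intervals that allow for repeated pairs: a mixed model, repeated-measures limits of agreement, or a patient-level bootstrap.
- If the study is to conclude that SpHb is accurate enough, specify and justify a margin in advance. Otherwise state that agreement is reported as estimation only.
- Keep correlation, tracking of changes in Hb and the absorbance analysis as secondary or exploratory, and state which variables the absorbance analysis relates.

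The cost is wording and a clustered method, with no new data or procedures. A margin, if wanted, needs clinical justification and takes more work. The headline result may look less favourable than r, and the correct intervals will be wider than ones that ignore clustering.

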## **1.2 Study Devices**

The Masimo Radical-7 is a noninvasive monitor that measures arterial oxygen saturation (SpO2), pulse rate (PR), and perfusion index (PI), along with optional measurements of hemoglobin (SpHb), carboxyhemoglobin (SpCO®), total oxygen content (SpOC), methemoglobin (SpMet), Pleth Variability Index (PVI®), Oxygen Reserve Index (ORI™), Acoustic Respiration Rate (RRa®), and Pleth Respiration Rate (RRp). Masimo SET® technology is clinically proven to satisfy all sensitivity and specificity requirements for pulse oximetry. Masimo rainbow® technology uses 7+ wavelengths of light to continuously and noninvasively measure carboxyhemoglobin (SpCO), methemoglobin (SpMet), and total hemoglobin (SpHb®), as well as providing a more reliable probe-off detection. Total oxygen content (SpOC) provides a calculated measurement of the amount of oxygen in arterial blood, which may provide useful information about oxygen both dissolved in plasma and combined with hemoglobin. Perfusion Index (PI) with trending capability indicates arterial pulse signal strength and may be used as a diagnostic tool during low perfusion. Pleth Variability Index (PVI) may show changes that reflect physiologic factors such as vascular tone, circulating blood volume, and intrathoracic pressure excursions. [The utility of PVI is unknown at this time and requires further clinical studies. Technical factors that may affect PVI include probe malposition and patient motion.] Oxygen Reserve Index (ORI) is an index measured noninvasively and continuously to provide an earlier indication of impending hypoxia by extending oxygen monitoring of pulse-oximetry to the moderate hyperoxic regions. Respiration rate can be determined by the acoustic (RRa) or plethysmographic waveform (RRp). [REDACTED]

FastSat® tracks rapid changes in arterial O2. A detailed description of the Masimo Radical-7 can be found in the attached manual.

Masimo Rainbow sensors: a finger probe that consists of a series of light emitting diodes (LEDs) and photodetectors. First, light is emitted through a capillary bed; then, the sensors detect the transmitted light. The signals from the sensor are processed and used to quantify hemoglobin levels noninvasively.

Data acquisition system: consists of a hardware component connected to a laptop with data collection software used to capture wavelength data.

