## **6.6 Time Table and Costs**

Study will continue until enrollment target has been met and subject data is collected. No inducement for participation is offered to patient's legal representatives. There are no added monetary costs to the patient related to participation in this protocol. It is routine care to place arterial catheters in ventilated critically ill adult patients, especially if they are anemic or require frequent lab checks. Masimo engineers will analyze the data, and aggregate data will be provided to the LLU Anesthesiology Department for analysis, presentation and possible publication.

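### Section 6.5 sets hemoglobin against spectral absorbance and never names SpHb, so read literally it does not carry out the validation stated in Sections 2 and 6.3

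*Combined protocol and SAP*

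**What the plan says.** Section 6.5 devotes one sentence to Hb. The analysis is to determine "the correlation between changing hemoglobin concentrations determined by the 3 different methods and spectral absorbance". SpHb does not appear in it, the three methods are not listed there or in any other visible section, and correlation is the only statistic named.

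Other sections describe a different comparison:

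- **Section 2, design:** "Noninvasive pulse oximetry-determined SpHb will be compared to ABG co-oximetry and research lab equipment-determined Hb values".
- **Section 2, goal:** to "establish the correlation of Hb values determined by the SpHb system with Hb as measured by other validated devices".
- **Section 6.3, purpose of the extra blood:** "Additional blood sampling is necessary to validate the SpHb system". The extra sample is 4 mL at up to 10 draws, so at most 40 mL per patient.
- **Section 6.3, data recorded:** "SpHb will be recorded with each blood draw sample". The extra sample is "sent for cell count and cyanomethemoglobin determination by Masimo laboratories".

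Four further facts bear on the point. Section 1.2 separates the light signal from the SpHb value ("The signals from the sensor are processed and used to quantify hemoglobin levels noninvasively") and says that wavelength data are captured. Section 5 describes prototype sensors. Section 6.6 says "Masimo engineers will analyze the data", with aggregate data going to the site. Section 4.3 gives enrollment as up to 600, with no derivation.

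**The concern.** A validation study has to test the number that the clinician will read. Section 6.5 instead names the optical input from which that number is computed. An analyst who followed the sentence as written could report a strong Hb–absorbance relation and leave the accuracy of SpHb unexamined, although the paired data exist. Section 1.3 looks ahead to the system being accurate enough to replace invasive Hb measurement, so accuracy of the displayed value is the result that matters.

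There is a secondary issue. Relating reference Hb to absorbance is also a step used in building or retuning an algorithm. The sponsor will hold the wavelength data and the reference values, and the visible text does not say whether spectra from these patients may be used in that way. If they were, and accuracy were then quoted from the same patients, the error would look smaller than it is in new patients.

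**Working it through.** **1. What the sentence can mean.** There are three readings.

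| Reading | What is analysed | Does it test displayed SpHb? |
|---|---|---|
| A. Three reference assays, each correlated with the absorbance signal | Reference Hb against the input to SpHb | No |
| B. SpHb is one of the three methods | SpHb against its own input, besides the references | No; the SpHb part is circular |
| C. Absorbance is a loose name for SpHb | Reference Hb against SpHb | Yes, but by correlation only |

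Reading A can be filled from the text: co-oximetry (Section 2), cell count and cyanomethemoglobin (6.3). Reading B can also be filled: SpHb, co-oximetry and research-laboratory Hb (Section 2). Reading C fits the design in Section 2. The wording alone points most naturally to A or B, because Section 1.2 treats signal and SpHb as different things.

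**2. Why a strong correlation would not settle accuracy.** No figure in the plan can be reproduced here: 6.5 gives no accuracy limit, SD or expected correlation. The illustration therefore uses assumed values: Hb SD 1.5 g/dL, error SD 0.8 g/dL, constant display bias *b*.

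- r = 1.5 / √(1.5² + 0.8²) = 1.5 / 1.70 = 0.88 for every *b*.
- RMS error = √(*b*² + 0.8²).
- Limits of agreement = *b* ± 1.96 × 0.8 = *b* ± 1.57.

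| Bias *b* (g/dL) | r | RMS error (g/dL) | Limits of agreement (g/dL) |
|---|---|---|---|
| 0 | 0.88 | 0.80 | −1.57 to 1.57 |
| 1 | 0.88 | 1.28 | −0.57 to 2.57 |
| 2 | 0.88 | 2.15 | 0.43 to 3.57 |

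Under reading A the gap is wider still. The conversion from absorbance to displayed value does not enter the correlation, so an error in it cannot show.

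For the circular part of reading B, assume absorbance noise equivalent to 1.0 or 2.0 g/dL and device noise of 0.3 g/dL.

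- SpHb with absorbance: √(2.25 + 1) / √(2.25 + 1 + 0.09) = 0.99, and √(2.25 + 4) / √(2.25 + 4 + 0.09) = 0.99.
- SpHb with reference: 1.5 / 1.83 = 0.82, and 1.5 / 2.52 = 0.60.
- Half-width of the limits of agreement: 1.96 × √1.09 = 2.0 g/dL, and 1.96 × √4.09 = 4.0 g/dL.

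The 0.99 follows from assuming that SpHb is computed from absorbance. It illustrates circularity and predicts nothing about this device.

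**3. How large the optimism could be if spectra were modelled on the same patients.** The model is an assumed linear fit with 10 readings per patient (the maximum in 6.3) and a residual intraclass correlation of 0.6. Seven terms matches the smallest wavelength count in Section 1.2; 40 terms is an assumption. The table gives the excess of the error in new patients over the apparent error.

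| Patients | 7 terms | 40 terms |
|---|---|---|
| 50 | 9% | 55% |
| 100 | 4% | 26% |
| 600 | about 0% | about 3% |

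These values assume that the spectral terms vary mostly between patients (intraclass correlation about 0.8). With 0.3, the figures at 50 patients fall to about 6% and 21%.

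As a cross-check with one independent reading per patient, apparent over new-patient RMSE is √((n − p − 1)/(n + p + 1)). For n = 600 and p = 7 this is √(592/608) = 0.987, an excess of 1%. For p = 50 it is √(549/651) = 0.918, an excess of 9%. So even at 600 patients the optimism depends on the number of spectral terms and the readings per patient.

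**The case against.** The strongest reply is that validation is planned. Section 2 states the SpHb comparison and makes it the goal, 6.3 records SpHb at every draw, and reading C makes 6.5 a loosely worded version of the same comparison. This stands in part. The comparison is under-specified in 6.5, not abandoned by the protocol. It does not remove the point: a sentence open to three readings, two of which miss the target, needs rewording, and reading C still supplies only a correlation.

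A reader might go further and infer that modelling Hb on spectra is the declared analysis, or that the sponsor intends to tune and validate on the same patients. The documents do not support that. Section 6.5 speaks only of correlation, and no visible passage says that an algorithm will be fitted or updated. The risk is inferred from wavelength capture, prototype sensors and analysis by the sponsor. Nor can a version lock or a held-out set be declared absent from the full plan: the material between Sections 2 and 4 is not in the text available for review, and parts of Sections 1.2, 5 and 8.3 are redacted.

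It is also fair to say that the large optimism figures come from patient and term counts that appear nowhere in the plan. That stands. Because 600 is a ceiling, and 6.1 allows up to eight sensors at various body sites, smaller subsets by sensor or site are possible, but the plan does not describe fitting to them.

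**Conclusion.** The point holds as a fault of specification. The one visible sentence on Hb analysis does not name the quantity to be validated, the comparators or a measure of agreement. Read literally, it cannot show that SpHb is accurate. This conclusion rests on the text and needs no assumed number. The figures for bias (r of 0.88 with RMS error from 0.80 to 2.15 g/dL) only show how little a correlation would reveal.

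Reuse of data is a lesser point: a possibility that the visible text leaves open, not a plan that it states. Under the assumed models it would matter little with all 600 patients (about 0–3% for 7 to 40 terms with 10 readings each), and more with small subsets or many terms. The change should be made, because it costs little and the pairs are already being collected. Confidence is medium, since removed and redacted text may hold relevant detail.

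**What to change.** Replace the first sentence of 6.5 with wording such as:

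*The Hb validation analysis compares the SpHb value output at each blood draw with each reference measured on that draw: ABG co-oximetry, laboratory cell-count Hb and cyanomethemoglobin. For each reference, bias and 95% limits of agreement are reported with confidence intervals, from a model of the paired differences with between-patient and within-patient components of variance. Correlation is descriptive.*

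Then add:

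*The sensor type and the sensor and software versions are recorded on the CRF for each patient. Any analysis of Hb against spectral absorbance is separate and is not reported as validation. If spectra from these patients are used to develop or retune the algorithm, accuracy is reported only from patients not used for that work, with the split made by patient and not by reading.*

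If cell-count Hb means the clinical CBC as well as the sponsor's laboratory result, the text should say which is which.

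The cost is wording and a version field on the CRF, where Section 5.1.2 already documents device and sensor use. No extra blood or patients are needed. The one downside is conditional: if the algorithm is developed on these data, fewer patients support the accuracy claim and its interval is wider. If no development is planned, that clause costs nothing.

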### 6.4 Data Collection

Additional data collection for this study will include demographics such as age, height, weight, [REDACTED] (skin tone), site dimensions (e.g. finger diameter for finger sensor, alar thickness for nose sensor), pre-existing comorbidities, surgical procedures performed [REDACTED] and ASA status, medications. Volumes of fluid input (blood, albumin, crystalloid) and output (estimated blood loss, urine output) will also be recorded. Other de-identified data such as ventilator settings, may be collected for data analysis. Hospital records, clinical and office charts, laboratory notes, memoranda, recorded data from automated instruments, and copies or transcriptions certified after verification as being accurate and complete may be accessed to obtain above defined data.

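### Section 6.5 prespecifies no confounder adjustment for the transfusion and fluid versus outcome correlation, although these treatments are given by clinical status and Hb

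*Combined protocol and SAP*

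**What the plan says.** Section 6.5 (Data Analysis) closes with two outcome analyses. The first reads "Outcome data will be analyzed for any relationships between the inciting event, blood loss and outcome markers", and its purpose is to see whether inciting factors predict outcome. The second is to look for "any correlation between transfusion and fluid management variables on outcome". The visible text gives no regression model, covariates, exposure window or limit on interpretation for either.

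Other sections bear on the second analysis:

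- Section 6.3: "All decisions regarding fluid management and the need for transfusion will be at the discretion of the attending physicians", and these decisions "will be based on the results of the clinical status and Hb measured by CBC as is customary for transfusion".
- Section 2: the study is a "prospective, nonrandomized, sequential data collection study". Its stated goal is to correlate SpHb, ORI and PVI with reference measurements. The outcome analysis is not part of that goal.
- Section 1.1: low Hb is linked to worse outcome, and so is receipt of transfusion. Both too little and too much intravascular volume are described as potentially harmful.
- Section 6.3: "Each patient enrolled in this trial will have Hb measured and recorded prior to data collection".
- Section 6.4: age, "pre-existing comorbidities, surgical procedures performed", ASA status, fluid and blood volumes given, and estimated blood loss are recorded. Nothing connects them to the outcome analysis.
- Section 4.3: enrollment may reach 600. This is a ceiling, and no calculation supports it.

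**The concern.** Treatment here responds to prognosis. A patient is transfused because Hb is low or clinical status is poor, and section 1.1 itself links low Hb to worse outcome. Nothing in the design breaks that link. A crude correlation therefore mixes any effect of transfusion or fluid with the reasons for giving it. The preposition in the plan's wording (management variables on outcome) invites the reader to take the result as an effect.

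A larger cohort does not help. It narrows the interval around a biased value and so makes a spurious finding more likely to reach significance.

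Two features raise the stakes for an otherwise secondary analysis. Section 1.1 suggests that continuous Hb monitoring could limit the number of units transfused, so a spurious transfusion-harm signal would appear to support the device's rationale. Section 6.6 has the sponsor's engineers analyze the data and pass aggregate data to the department for possible publication. Aggregates do not allow patient-level adjustment later, although copies of the case report forms stay on site (section 8.2).

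**Working it through.** The plan gives no alpha, power, effect size or event rate for this analysis, so it has no figure to reproduce. The checks below show how large the bias could be. Only the 600 comes from the documents (section 4.3). The smaller sample sizes, the confounding strengths and the two-sided 5% level are assumptions.

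**1. Spurious correlation when treatment has no effect.** Let severity S have correlation a with treatment T and b with outcome Y, and let T have no effect on Y. Then r(T,Y) = a × b. With d = atanh(r) × √(n − 3), the chance of a significant result in either direction is Φ(d − 1.96) + Φ(−d − 1.96). At n = 600, √597 = 24.43, and |r| above 0.080 is significant.

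| n | a = b | r = a × b | d | Chance of p < 0.05 |
|---|---|---|---|---|
| 600 | 0.2 | 0.04 | 0.978 | 0.163 + 0.002 = about 16% |
| 600 | 0.3 | 0.09 | 2.205 | about 60% |
| 600 | 0.4 | 0.16 | 3.943 | about 98% |
| 200 | 0.3 | 0.09 | 0.0902 × 14.04 = 1.267 | 0.244 + 0.001 = about 24% |

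With no confounding the chance is 5%.

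**2. A different model: simulated logistic regression.** True treatment OR is 1. Assumed: 40% treated and 20% events at average severity, the same OR per SD of severity for treatment and for outcome, and 600 replicates per row. The last column counts significant harm only, for which the nominal rate is 2.5%.

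| n | Severity OR per SD | Median crude OR | Significant harm, crude |
|---|---|---|---|
| 600 | 1.25 | 1.05 | 4% |
| 600 | 1.5 | 1.17 | 12% |
| 600 | 2 | 1.48 | 51% |
| 600 | 2.5 | 1.84 | 90% |
| 300 | 2 | 1.47 | 30% |
| 100 | 2 | 1.57 | 13% |

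**3. Direction.** If sicker patients receive less of the treatment (OR 0.5 per SD for treatment, 2 for outcome, n = 600), the crude OR is 0.66. Significant benefit then appears in 51% of runs and significant harm in none.

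**4. What adjustment achieves.** If the recorded covariates capture a share q of severity variance, the partial correlation is ab(1 − q) / √[(1 − a²q)(1 − b²q)]. At n = 600, with d = atanh(partial r) × √596:

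| a = b | q | Partial r | Chance of p < 0.05 |
|---|---|---|---|
| 0.4 | 0.8 | 0.032 / 0.872 = 0.037 | about 15% |
| 0.4 | 0.5 | 0.080 / 0.920 = 0.087 | about 57% |
| 0.5 | 0.8 | 0.050 / 0.800 = 0.063 | about 33% |
| 0.5 | 0.5 | 0.125 / 0.875 = 0.143 | about 94% |

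The simulation agrees in kind. At severity OR 2 and n = 600, adjusting for perfectly measured severity gives OR 0.99 and significant harm in 1.5% of runs. With severity measured at reliability 0.8 the figures are 1.11 and 7.7%; at 0.5 they are 1.27 and 22.3%.

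**The case against.** The strongest reply is that this is one closing clause outside the stated goal, with no hypothesis, alpha or claim attached, and that a descriptive correlation is legitimate if it is read as one. That is fair as to importance: no device comparison depends on it. But section 6.5 does not label the analysis descriptive, and its wording suggests an effect.

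Several stronger readings are tempting and are not supported:

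- *The analysis is unadjusted.* Section 6.5 does not say so. It states correlation and is silent on adjustment, so the supportable statement is that none is prespecified.
- *It will show harm.* The chance of significant harm at 600 patients runs from about 4% to 90% across the simulated strengths, and 600 is a ceiling. Sections 4.1 and 4.2 require ventilation and an arterial line and exclude extreme instability, which may narrow the range of severity and weaken the confounding.
- *Fluid will also look harmful.* No section says sicker patients receive more fluid. Section 1.1 treats both extremes of volume as harmful, so the relation need not be monotone, and step 3 shows the sign can reverse.
- *The predictive analysis is invalid too.* Predictive value in section 6.5 attaches to inciting factors. Confounding does not by itself invalidate prediction.

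It can also be said that regression is no cure. That stands: step 4 shows substantial residual error when severity is poorly captured. No severity-of-illness score is visible, and a model adjusted only for baseline ignores later Hb, which also drives transfusion. Lastly, the text between sections 2 and 4 was not available and section 6.4 is partly redacted, so outcome definitions or further covariates may exist there.

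**Conclusion.** The concern holds in a limited form. The plan states correlation as the method for an association between discretionary, prognosis-driven treatment and outcome, and prespecifies neither adjustment nor a limit on interpretation. For transfusion, apparent harm is the likely direction, because the protocol makes Hb a basis for transfusion and links low Hb to worse outcome. For fluid the result is open to bias of unknown sign.

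The size depends on assumed confounding. With no true effect and equal severity correlations, a spurious significant result at 600 patients has a chance of about 16% (0.2), 60% (0.3) or 98% (0.4), and less with fewer patients. These figures illustrate the mechanism and do not predict this study's result. The point should be addressed before analysis, but it does not touch the SpHb, ORI or PVI comparisons.

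**What to change.** Amend section 6.5 as follows:

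1. Name the outcomes and the exposure window.
2. Beside the crude correlation, report a patient-level regression of each outcome on transfusion and fluid volume. Adjust for pre-treatment covariates already recorded: pre-study Hb, age, ASA status, comorbidities, and ICU unit or procedure.
3. Use estimated blood loss as a covariate only where it can be timed before the exposure. Section 6.4 does not visibly record that timing.
4. State that the results are descriptive associations, that residual confounding by indication remains, and that no causal claim about transfusion or fluid management will be made. Given step 4 of the working, this statement matters as much as the regression.
5. Leave the separate clause on the predictive value of inciting factors as it is.

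Because section 6.6 passes only aggregate data to the department, the adjusted model should be written into the sponsor's own analysis.

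The listed covariates need no new data collection. The work is analysis wording, plus defining the outcomes if they are not defined in text that was not visible. The price is slightly wider intervals, a weaker headline association, and bias that is reduced rather than removed.
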